12. DATA HANDLING AND RECORD KEEPING

12.1 Source data

Source data is defined as all information in original records and certified copies of original records of clinical findings, observations, or other activities in a clinical trial necessary for the reconstruction and evaluation of the trial. In order to allow for the accurate reconstruction of the trial and clinical management of participants, source data will be accessible and maintained.

Table 7: Source data in ECAL trial

Data	Source
Patient reported data (questionnaires)	This may be paper or electronic. If completed on paper, the original participant-completed paper form is the source data. If completed directly into the REDCap database, this electronic record is the source.
Baseline, behavioural support call and Follow up data	Data is entered directly into the ECAL trial system which is the source data however details will also be kept in medical notes. It is held on BCTU servers on the REDCap data entry system. (If paper copies are used these will be the source).
Lab results (FBC, Toxicant analysis, biomarkers, cotinine)	The original records (which may be electronic) is the source data and will be kept and maintained, in line with normal local practice. Information will be transcribed onto CRFs.
Bronchodilator spirometry tests	The original records, which may be electronic records, are the source data. They will be kept and maintained in line with normal local practice. Information will be transcribed onto CRFs.
Clinical event data	The original clinical annotation is the source document. This may be found on clinical correspondence, or electronic or paper participant records. Clinical events reported by the participant, either in or out of clinic (e.g. phone calls), must be documented in the source documents.
Trial-specific event data	The main trial CRF is the source for data that would otherwise not routinely be recorded in the patient's medical records.
Recruitment	The original record of the randomisation is the source. It is held on BCTU servers as part of the randomisation and data entry system.
Withdrawal	Where a participant expressed a wish to withdraw, the conversation must be recorded in the source data.

12.2 Case Report Form (CRF) completion

The CRFs will include (but will NOT be limited to) the following Forms (see table 8).

Table 8: Case report forms in the ECAL trial

CRF Name	Schedule for completion at site	Schedule for submission to BCTU
Consent to contact	Patient expression of interest in the trial (direct to site)	Immediately if entered onto study database, or if paper as soon as possible after consent to contact being given

CRF Name	Schedule for completion at site	Schedule for submission to BCTU
Pre-baseline check	Pre-baseline check prior to baseline appointment booking	Immediately if entered onto study database, or if paper as soon as possible after pre-baseline assessment
Informed Consent form	Baseline assessment visit	As soon as possible after baseline assessment visit
Baseline Assessment Visit	Baseline assessment visit	Immediately if entered onto study database, or if paper as soon as possible after the baseline assessment visit
Randomisation	Baseline assessment visit	Immediately if entered onto study database, or if paper as soon as possible after the participant has been randomised
Baseline Blood Results: Full Blood Count (FBC)	Upon receipt of baseline FBC blood results	as soon as possible after the Baseline assessment visit
Pre-quit day	- 1 week behavioural support call	Immediately if entered onto study database, or if paper as soon as possible after telephone behavioural support
Quit day call	Quit day behavioural support call	Immediately if entered onto study database, or if paper as soon as possible after telephone behavioural support
Weekly +1w, +2w, +3w Post Quit Day	+1 week, +2 week, +3 week behavioural support calls	Immediately if entered onto study database, or if paper as soon as possible after telephone behavioural support
Weekly +4w Post Quit Day	+4 week behavioural support call	Immediately if entered onto study database, or if paper as soon as possible after telephone behavioural support
26 week	26 week follow up call	Immediately if entered onto study database, or if paper as soon as possible after the Week 26 visit
52 week	52 week follow up visit	Immediately if entered onto study database, or if paper as soon as possible after the Week 52 visit
52 week Blood Results: Full Blood Count (FBC)	Upon receipt of 52 week FBC blood results	As soon as possible after the Week 52 visit
Serious Adverse Event Form	On becoming aware of an SAE	Immediately if entered onto study database, or if paper as soon as possible after, or if paper emailed to BCTU within 24 hours of research staff at site becoming aware of event
Withdrawal Form	On patient request	At the point of discontinuation or withdrawal

A CRF should be completed for each individual participant.

In all cases it remains the responsibility of the PI to ensure that the CRF has been completed correctly and that the data are accurate. This will be evidenced by the signature of the PI, or delegate(s). The Site Signature & Delegation Log will identify all those personnel with responsibilities for data collection.

The delegated staff completing the CRF should ensure the accuracy, completeness and timeliness of the data reported. This will be evidenced by signing and dating the CRF.

Data reported on each CRF will be consistent with the source data and any discrepancies will be explained. All missing and ambiguous data will be queried. Staff delegated to complete CRFs will be trained initially via a site initiation meeting or by other trained members at each site to adhere to procedures.

The following guidance applies to data and partial data:

- Only CRFs provided by the Trial Office should be used.
- Original completed CRFs or true copies should be sent to the Trial Office with copies filed in the ISF.
- Entries should be made in dark ink and must be legible.
- Any errors should be crossed out with a single stroke, the correction inserted and the change initialled and dated.
- Time format – all times should be in accordance with the 24hr clock
- Rounding conventions – rounding should be to the nearest whole number: If the number you are rounding is followed by 5, 6, 7, 8, or 9, round the number up. **Example:** 3.8 rounded to the nearest whole number is 4. If the number you are rounding is followed by 1, 2, 3 or 4, round the number down. **Example:** 3.4 rounded to the nearest whole number is 3
- Trial-specific interpretation of data fields – where guidance is needed additional information will be supplied
- Entry requirements for concomitant medications (generic or brand names) – generic names should be used where possible
- Missing/incomplete data – should be clearly indicated – all blank fields will be queried by the Trial Office
- Repeat laboratory tests – the data used to inform clinical decisions should always be supplied. If a test is repeated it is either to confirm or clarify a previous reading. Confirmatory tests should use the original test values.
- Protocol and GCP non-compliances should be reported to the Trial Office on discovery.

On completion of paper CRFs, a copy or a scan of each form will be submitted to the Trial Office for entry into the database by the data manager and the original filed in the ISF. Electronic CRFs will be directly entered onto the REDCap trial database by a delegated member of site staff or trial team member.

12.3 Participant completed questionnaires

Participant completed questionnaires can be completed in clinic, during behavioural support calls or via postal paper questionnaires.

Participants will complete a questionnaire at baseline, +4 weeks behavioural support telephone call, 26 weeks and 52 weeks after TQD. The following validated questionnaires will also be used as an assessment of health and quality of life for patients with COPD:

- Mood and physical symptom score (MPSS) for measuring nicotine withdrawal symptoms.
- COPD assessment test (CAT).
- Hospital anxiety and Depression Scale (HADS)
- Clinical COPD Questionnaire (CCQ) for measuring COPD symptoms.
- EQ-5D-5L for measuring quality of life for the economic evaluation.
- Fagerström Test for Nicotine Dependence (FTND)

A bespoke resource use questionnaire developed from existing COPD resource use questionnaires will be completed at 26-week and 52-week for the economic evaluation.

Baseline and 52-week questionnaires will be completed on paper. Data collected on paper forms will then be transcribed onto the REDCap data capture system by a delegated member of site staff or the Trial Office. If for any reason a Baseline or 52-week questionnaire has not been completed during the clinic visit, an MDC questionnaire will be collected via post and transcribed into the REDCap database.

Participant questionnaires at +4 weeks behavioural support telephone call and 26 week follow up can be completed by telephone with the support of the smoking cessation advisor. If necessary, an MDC 4+ week or 26-week questionnaire will be sent via post to a participant for completion.

If completed in clinic, the questionnaire should be completed by the participant alone but physical assistance in completing the form can be given by site staff or the participant's friends and relatives where appropriate. In such circumstances, questions are to be read to the participant verbatim and the responses must not be led by the person assisting with the completion. This requirement should be made clear when the participant's friends and relatives are helping.

Participants should be encouraged to respond to all questions but can refuse to answer any, or all, of the questions should they wish. Where a questionnaire is returned to site staff, in person, with some questions unanswered, site staff should clarify with the participant that they have chosen not to respond specifically to the unanswered questions and that they have not simply missed them in error.

If completed via post, a paper questionnaire should be completed by the participant directly who will be asked to return it to the trial office in a pre-paid envelope. Upon receipt, a member of the trial team will check the completed questionnaire and can contact the participant by telephone, post, or email to query any missing data.

If completed on-line, an electronic version of the questionnaire will be completed by a member of the QMUL trial team under the direction of the participant. Upon submission, the Trial Office will check the completed questionnaire and can contact the participant by telephone, post or email to query any missing data.

If completed by remote video or telephone, the questionnaire will be completed by a member of the QMUL trial team under the direction of the participant. The questions are to be read to the participant verbatim and the responses must not be led by the trial team member conducting the remote video or telephone call. The participant will be encouraged to answer the questions as fully as they can.

12.4 Data management

Processes will be employed to facilitate the accuracy and completeness of the data included in the final report. These processes will be detailed in the trial specific Data Management Plan and include the processes of data entry, data queries and self-evident corrections on trial data.

Where possible, trial data will be entered directly into the REDCap trial database, by a delegated member of site staff or the trial team, with the exception of paper reply slips and questionnaires. If online data collection is not possible for any reason, a paper version of the document will be completed and transcribed into the REDCap trial database by the site or Trial Office.

The REDCap data capture system will conduct automatic range checks for specific data values to ensure high levels of data quality. Queries will be raised via the REDCap trial database, with the expectation that these queries will be completed by the site within 30 days of receipt.

12.5 Self-evident corrections

The below self-evident corrections will be permitted on paper CRFs by the Trial Office:

- **Contingent fields:** When a response to a question determines, to a degree, the response required by a second question, then conflicts in the responses can be resolved by the data entry clerk e.g. Has the person had procedure “x”? If yes, state type. If the response to the first question is “no”, yet the type of procedure is stated, it is self-evidently true that the initial response was incorrect.

12.6 Data security

UoB has policies in place which are designed to protect the security, accuracy, integrity and confidentiality of Personal Data. The trial will be registered with the Data Protection Officer at UoB and will hold data in accordance with the Data Protection Act (2018 and subsequent amendments). The Trial Office has arrangements in place for the secure storage and processing of the trial data which comply with UoB policies.

The Trial Database System incorporates the following security countermeasures:

Physical security measures: restricted access to the building, supervised onsite repairs and storages of back-up tapes/disks are stored in a fire-proof safe.

Logical measures for access control and privilege management: including restricted accessibility, access controlled servers, separate controls of non-identifiable data.

Network security measures: including site firewalls, antivirus software and separate secure network protected hosting.

System management: the system will be developed by the Programming Team at the Trial Office, and will be implemented and maintained by the Programming Team.

System design: the system will comprise of a database and a data entry application with firewalls, restricted access, encryption and role-based security controls.

Operational processes: the data will be processed and stored within BCTU (University of Birmingham).

System audit: The system will benefit from the following internal/external audit arrangements:

- Internal audit of the system
- Periodic IT risk assessment

Data Protection Registration: UoB's Data Protection Registration number is Z6195856.

12.7 Archiving

Archiving will be authorised by the ECAL trial office at BCTU on behalf of the Sponsor following submission of the end of trial report.

It is the responsibility of the PI to ensure all essential trial documentation and source documents (e.g., signed ICFs, Investigator Site Files, Laboratory Files, participants' hospital notes, copies of CRFs) at their site are securely retained for the contractual period. Archiving will be authorised by BCTU on behalf of UoB following submission of the end of trial report. No documents should be destroyed without prior approval from the Sponsor or their delegate.

The TMF will be stored at BCTU for at least 3 years after the end of the trial. Long-term offsite data archiving facilities will be considered for storage after this time; data will be stored securely and confidentially for at least 25 years. BCTU has standard processes for both hard copy and computer database legacy archiving.

13. QUALITY CONTROL AND QUALITY ASSURANCE

13.1 Site set-up and initiation

All PIs will be asked to sign the necessary agreements including Protocol PI signature page and a trial Site Signature and Delegation log between the PI and the Trial Office and supply a current CV and GCP certificate. All members of the site research team are required to sign the Site Signature and Delegation Log, which details which tasks have been delegated to them by the PI. The Site Signature and Delegation Log should be kept up to date by the PI. It is the PI's responsibility to inform the Trial Office of any changes in the site research team.

Prior to commencing recruitment, each recruiting site will undergo a process of site initiation, either a face-to-face meeting or via teleconference, at which key members of the site research team are required to attend covering aspects of the trial design, protocol procedures, adverse event reporting, collection and reporting of data and record keeping. Sites will be provided with an ISF and a Laboratory File containing essential documentation, instructions, and other documentation required for the conduct of the trial.

13.2 Monitoring

The central and on-site monitoring requirements for this trial have been developed in conjunction with the trial specific risk assessment and are documented in the trial specific monitoring plan.

13.2.1 On-site monitoring

For this trial, all sites will be monitored in accordance with the trial risk assessment and monitoring plan. Any monitoring activities will be reported to the Trial Office and any issues noted will be followed up to resolution. Additional on-site monitoring visits may be triggered. PIs and site research teams will allow the ECAL trial staff access to source documents as requested. The monitoring will be conducted by BCTU/UoB or Sponsor staff.

13.2.2 Central monitoring

The Trial Office will check received ICFs and CRFs for compliance with the protocol, data consistency, missing data and timing at a frequency and intensity determined by the Data

Management Plan. Sites will be sent queries through the REDCap trial database requesting missing data or clarification of inconsistencies or discrepancies.

13.2.3 *Sample monitoring*

Remote monitoring of sites regarding collection and management of blood samples will be conducted by BCTU via reviewing relevant CRFs. On-site monitoring will be triggered should there be a high amount of missing data for full blood count, and if there is a high rate of haemolysis in samples returned.

Long term sample storage at the primary site (University of Birmingham Research Laboratories, QEHB) will be monitored for temperature variance which may impact sample integrity 24 hours a day by electronic monitoring system, with established notification hierarchy should freezer temperature move beyond pre-set limits. Samples collected and electronic monitoring records will be maintained for 5 years after collection. Sample storage will be recorded in ECAL lab file, maintained by the EME safety sub-study technician.

13.2.4 *Central stop smoking service/ pharmacy monitoring*

The Trial Office will check products dispense log for compliance with what has been requested at a frequency and intensity determined by the Data Management Plan. Further monitoring will be triggered should there be a high amount of inconsistent or missing data on products allocated.

13.3 Audit and inspection

The Investigator will permit trial-related monitoring, audits, ethical review, and regulatory inspection(s) at their site and provide direct access to source data/documents. The Principal Investigator will comply with these visits and any required follow-up. Sites are also requested to notify the Trial Office of any relevant inspections or local audits.

13.4 Notification of Serious Breaches

In accordance with the Medicines for Human Use (Clinical Trials) Regulations 2004 and its amendments, the Sponsor of the trial is responsible for notifying the licensing authority in writing of any serious breach of the conditions and principles of GCP in connection with that trial or of the protocol relating to that trial, within 7 days of becoming aware of that breach. For the purposes of this regulation, a “serious breach” is a breach which is likely to affect:

- the safety or physical or mental integrity of the participants of the trial;
- the scientific value of the trial.

Sites are therefore requested to notify the Trial Office of any suspected trial-related serious breach of GCP and/or the trial protocol as soon as they become aware of them. Where the Trial Office is investigating whether or not a serious breach has occurred, sites are also requested to co-operate with the Trial Office in providing sufficient information to report the breach to the MHRA where required and in undertaking any corrective and/or preventive action.

14. END OF TRIAL DEFINITION

The end of trial will be the date of the last data capture including resolution of data queries. This will allow sufficient time for the completion of protocol procedures, data collection and input and data cleaning. The Trial Office will notify the REC, MHRA and the Sponsor within 90 days of the end of trial. Where the trial has terminated early, the Trial Office will notify the MHRA and REC within 15 days of the end of trial. The Trial Office will provide the REC, MHRA and the Sponsor with a summary of the clinical trial report within 12 months of the end of trial.

15. STATISTICAL CONSIDERATIONS

15.1 Sample size

The justification for the sample size is based on a control group event rate of 8%. This is the expected proportion of participants who will have quit smoking at 52 weeks using combination NRT and behavioural support. The most recent data from specialist stop smoking services report a 10% quit rate with varenicline and behavioural support at 52 weeks, and combination NRT has been shown in a network meta-analysis to have similar effectiveness to varenicline.⁵⁶ However, quit rates are generally lower in COPD patients than in the general population⁸ and so a value of 8% was deemed clinically appropriate.

To detect a difference of 6% (i.e. a quit rate of 14%) between the combination NRT and EC arms using the standard method of difference between proportions and assuming 90% power and a type I error rate of 5%, a total of 603 participants per group will need to be randomised, 1206 in total. Assuming and adjusting for a 3% loss to follow-up/ drop-out rate (based on local cohort data for mortality) and rounding up, 1250 participants will need to be recruited.

15.2 Analysis of outcomes

A Statistical Analysis Plan (SAP) for the trial will be produced and will provide a more comprehensive description of the planned statistical analyses for the trial. A brief outline of these analyses is given below.

The primary comparison groups will be composed of those randomised to the control treatment (combination NRT and behavioural support) versus those randomised to the intervention (Electronic cigarette and behavioural support). In the first instance, all analyses will be based on the intention to treat principle, i.e. all participants will be analysed in the treatment group to which they were randomised irrespective of adherence or other protocol deviation. For all outcomes, appropriate summary statistics and differences between groups, e.g. mean differences, relative risks will be presented, with 95% confidence intervals and p-values from two-sided tests also given. Outcomes will be adjusted for the minimisation variables listed in section 7.1.1 where possible. No adjustment for multiple comparisons will be made.

15.2.1 *Primary outcome(s)*

The primary outcome for the ECAL trial is smoking abstinence since the TQD biologically validated (exhaled CO<8ppm) at 52 weeks post quit date. This will be measured in accordance with the Russell Standard¹ which is the accepted standard for smoking abstinence in trials of smoking cessation interventions.

The data for this outcome are binary, and therefore will be summarised using the number and percentage of participants in each category by intervention arm. An adjusted relative risk and 95% confidence interval will be estimated from a log-binomial regression model and the p-value from the associated model will be produced and used to determine statistical significance. We will also present the adjusted risk difference and the corresponding 95% confidence interval.

15.2.2 *Secondary outcomes*

The secondary outcomes consist of continuous, binary, and count data types.

Secondary outcomes that are binary in nature will be analysed using the same statistical methods described above for the primary outcome.

Secondary outcomes that are continuous will be summarised using the mean and standard deviation for each intervention arm. Minimum and maximum values will also be presented. The

difference between the group means and associated 95% confidence intervals at each time-point will be estimated through the use of a repeated measures mixed-effects linear regression model. All post-randomisation assessment times will be included. Parameters allowing for participant, treatment group, time variable, the randomisation minimisation variables and the baseline score will be included (all as fixed effects). Time will be assumed to be a categorical (fixed) variable. To allow for a varying treatment effect over time, a time by treatment interaction parameter will be included in the model. Estimates of differences between groups at each post-randomisation time-point will be taken from the model including this interaction parameter. Results will be presented as an adjusted mean difference and the associated 95% confidence interval. Longitudinal plots of the data over time will be constructed for visual presentation of the data.

Secondary outcomes that involve count data will be analysed using a Poisson regression model (or negative binomial regression if there is evidence of overdispersion) with an offset for the length of time the participant was in the trial included in the model, to obtain an adjusted incidence rate ratio and 95% confidence interval. The p-value from the associated model will be produced and used to determine statistical significance.

Validated questionnaires will be scored using the methods recommended by the authors.

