7.1 Randomisation process

After informed consent has been received, eligibility has been confirmed, and baseline assessments have been completed, the participant can be randomised into the trial using the REDCap trial database (see section 10.3 for baseline procedures).

Randomisation will be provided via the trial database using a secure online system (available at <https://bctu-redcap.bham.ac.uk>), thereby ensuring allocation concealment. Unique log-in usernames and passwords will be provided to those who wish to use the online system and who

have been delegated the role of randomising participants into the trial as detailed on the ECAL Site Signature and Delegation Log. These unique log-in details must not be shared with other staff and in no circumstances should staff at sites access either system using another person's login details. The online system will be available 24 hours a day, 7 days a week, apart from short periods of scheduled maintenance which sites will be informed of in advance.

In the event of the online system not being available, a back-up telephone toll-free randomisation service ([name]) is available Monday to Friday, 09:00 to 17:00 UK time, except for bank holidays, government guided closures and University of Birmingham closed days.

Participants will be randomised at the level of the individual in a 1:1 ratio to either the intervention (EC) or comparator (NRT). A minimisation algorithm will be used within the online randomisation system to ensure balance in the treatment allocation over the following key potential confounding variables:

- COPD stage (levels: stage 1-2 and stage 3- 4 based on FEV₁)
- Age (levels: 35-65, 66+ years)
- Sex at birth (levels: male, female)
- Fagerstrom test for nicotine dependence (FTND) score (levels: ≤6, 7+)

To avoid the possibility of the intervention allocation becoming predictable, a random element will be included in the algorithm. Full details of the randomisation specification will be stored in a confidential document at BCTU.

Participants randomised by error, i.e. randomised twice or found ineligible according to inclusion/exclusion criteria after randomisation, will be replaced to attain the full sample size.

Following randomisation, a confirmatory e-mail will be sent to the local PI, research nurse/delegated person who randomised the participant. The trial team will also receive a randomisation confirmatory e-mail.

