10.8 Spirometry

Participants will be asked to undergo a spirometric assessment at the baseline visit and at the 52 week follow up visit. Post-bronchodilator spirometry will be undertaken according to ATS/ERS 2019 guidelines⁵⁸ and carried out by practitioners trained to ARTP or ERS Standard. FEV1, FVC and MMEF will be measured using a verified/calibrated spirometer.

A pragmatic approach will allow sites to use the spirometry equipment available. To minimise the variability, all sites will be asked to use lab/desktop spirometers and if possible, use the same equipment at the baseline and the 52-week follow up visits. Details of the spirometry equipment make, model and date last calibrated/ verified will be recorded on the relevant CRFs.

It is also anticipated that there could be between-technician variability. Spirometry will be undertaken by trained site staff, some of whom undertake this as part of usual care. The trial team will ask sites to delegate lung function testing to ARTP certified staff. If this is not feasible, the trial team will provide spirometry training modelled on the ARTP standard. This training will be provided by an experienced professional. During this training those trained will have their spirometry outputs checked to ensure they achieve the correct level of competence before being delegated this role for the trial. During the trial, quality checks will also be performed on a sample of spirometry results from each participating site.

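### The model for continuous secondary outcomes is called mixed-effects but lists participant among its fixed effects; taken literally, the between-group differences it promises are not estimable

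*Protocol*

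**What the plan says.** Protocol section 15.2.2 says that the group differences and confidence intervals for continuous secondary outcomes are to be "estimated through the use of a repeated measures mixed-effects linear regression model". The same paragraph then sets out the model:

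- Responses: "All post-randomisation assessment times will be included". Baseline enters as a covariate, not as a response.
- Terms and their status: "Parameters allowing for participant, treatment group, time variable, the randomisation minimisation variables and the baseline score will be included (all as fixed effects"). Participant stands first in this list, and the parenthesis covers the whole list.
- Time: "Time will be assumed to be a categorical (fixed) variable".
- Interaction: "a time by treatment interaction parameter will be included in the model".
- Quantity to be reported: "Estimates of differences between groups at each post-randomisation time-point will be taken from the model including this interaction parameter".

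The paragraph names no random effect and no covariance structure for repeated values on the same person.

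Two other places matter. Section 7.1 fixes the unit of allocation: "Participants will be randomised at the level of the individual in a 1:1 ratio". Section 10.8 gives the lung-function schedule: "Participants will be asked to undergo a spirometric assessment at the baseline visit and at the 52 week follow up visit". Section 9.2.2 lists the continuous outcomes that fall under this model: MPSS at 1, 2, 3 and 4 weeks, CAT and CCQ at 4, 26 and 52 weeks, and FEV1, FVC and MMEF at 52 weeks.

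**The concern.** A mixed-effects model needs at least one random component, or its repeated-measures equivalent, a covariance structure within participant. Once participant is declared fixed along with everything else, neither is left, so the named model class and the list of terms cannot both be right.

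The choice between them is not cosmetic. Each person is in one arm throughout, so a separate fixed parameter for each participant absorbs everything that distinguishes one person from another, including the arm. What survives is how the difference between arms changes from one follow-up to the next. That is not what section 15.2.2 promises, which is the difference itself at each follow-up. To obtain the promised estimate, an analyst would have to depart from the written specification, and the model used for the symptom, withdrawal and lung-function comparisons would then not be the one pre-specified.

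**Working it through.** The plan states no figure on this point, so there is none to reproduce. The check is whether the promised contrast is estimable under the model as written.

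**Inputs.** Allocation by individual and four two-level minimisation factors (section 7.1); one baseline score, categorical time, a treatment-by-time interaction and post-randomisation responses only (section 15.2.2); T = 3 follow-ups for CAT and CCQ, 4 for MPSS and 1 for spirometry (section 9.2.2). The number of participants in the check, N = 200, is illustrative.

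**Algebra.** For participant i at time t, with arm z_i (0 or 1), minimisation variables x_i and baseline b_i:

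y_it = μ + α_i + τ·z_i + γ_t + δ_t·z_i + x_i′β + φ·b_i + error

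Here α_i is the fixed participant parameter, and δ is zero at the reference time. The difference between arms at time t is τ + δ_t. Add any constant c to τ and subtract c from α_i for every participant with z_i = 1. Every fitted value is unchanged, yet τ + δ_t has moved by c at every time. The data therefore cannot determine it. The same argument applies to the four β terms and to φ. Differences such as δ_t − δ_s do not move, so the interaction remains estimable where there are at least two follow-ups. The argument does not depend on N or on the pattern of missing visits.

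**Counts.**

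- Columns: intercept 1 + treatment 1 + time (T − 1) + interaction (T − 1) + minimisation 4 + baseline 1 + participant indicators (N − 1) = N + 2T + 4.
- Rank: N participant levels + (T − 1) + (T − 1) = N + 2T − 2.
- Deficiency: (N + 2T + 4) − (N + 2T − 2) = 6, namely treatment, the four minimisation variables and baseline.
- Residual degrees of freedom with complete data: NT − (N + 2T − 2).

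A numerical rank and estimability check with N = 200 gave the same values:

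| Outcome | T | Columns | Rank | Residual df | Time-point differences estimable |
|---|---|---|---|---|---|
| CAT, CCQ | 3 | 210 | 204 | 600 − 204 = 396 | 0 of 3 |
| MPSS | 4 | 212 | 206 | 800 − 206 = 594 | 0 of 4 |
| Spirometry | 1 | 206 | 200 | 200 − 200 = 0 | 0 of 1 |

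At the planned N = 1250 with T = 3 the formulas give 1250 + 6 + 4 = 1260 columns and rank 1250 + 6 − 2 = 1254, again 6 short.

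**After removing participant from the fixed part.** The design has full rank (11 of 11 columns for T = 3, 13 of 13 for T = 4, 7 of 7 for T = 1), and every time-point difference is estimable. A random-intercept fit to simulated data (N = 1250, T = 3, participant and residual standard deviations both assumed to be 4) gave a standard error of about 0.32 at each time. This agrees with the direct calculation √(2 × (16 + 16)/625) = √0.1024 = 0.32. The simulation shows only that the corrected model works; its variances are not trial figures.

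**The case against.** The best defence is that the paragraph shows its own intent. It names a mixed-effects model and asks for an adjusted difference at each follow-up. Both fit only if participant is the random or repeated unit and the remaining terms are fixed. Section 15.2 also calls itself a brief outline and defers detail to a SAP, where the choice between a random intercept and an unstructured covariance would normally be made. An analyst who did enter a parameter for each participant would see the aliasing at once.

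Most of this stands. It makes an innocent slip the likely explanation and keeps the matter small. It does not make the sentence right: the status of participant is not left open for the SAP but stated, and stated wrongly. A SAP that follows the sentence inherits the problem, and one that corrects it contradicts the protocol.

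A reader might infer more than the text supports:

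- *That the secondary analyses will fail, or that software output with a dropped or arbitrarily coded treatment term will be reported.* Nothing in the protocol indicates that the literal model would be fitted and reported unexamined, and the named model class points the other way.
- *That spirometry is a second, separate error.* The loss of all residual degrees of freedom follows from the same sentence, and the visit schedule in section 10.8 is not at fault. Once participant is no longer fixed, the model for one follow-up value reduces to ordinary linear regression.

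**Conclusion.** The point holds as an internal contradiction in the specification of one model. Read literally, section 15.2.2 makes the between-group difference non-estimable at every follow-up for CAT, CCQ, MPSS, FEV1, FVC and MMEF, and leaves the spirometry model saturated. This rests on participant being covered by the fixed-effects parenthesis, as the grammar requires, and on responses being post-randomisation only.

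The reach is limited. The primary outcome and the binary secondary outcomes use log-binomial regression, the count outcomes use Poisson or negative binomial regression, and the sample size rests on the difference in quit rates; none depends on this sentence. A random participant effect was probably intended. Whether the SAP already says so cannot be judged here, because it is not at hand. This is a wording correction that should be made before analysis.

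**What to change.** In section 15.2.2, confine the fixed effects to treatment group, categorical time, their interaction, the minimisation variables and the baseline score. State separately that participant is a random effect, or that correlation between repeated values is handled by a within-participant covariance structure. The choice of structure can stay with the SAP.

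Add one sentence for the outcomes with a single follow-up: for FEV1, FVC and MMEF, the 52-week value will be compared between arms by linear regression adjusted for the baseline value and the minimisation variables. Stating this avoids an instruction to fit an interaction with time that does not exist and a participant variance that one value per person cannot separate from residual error.

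The cost is two sentences in the protocol and matching text in the SAP. Data collection, conduct, sample size and participants are unaffected.
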